5.9.2 Modifications for events occurring during or immediately after ¹²⁴I- PEG-AVP0458 infusion

There is a potential for the occurrence of allergic-type reactions during and immediately following the administration of ¹²⁴I-labelled PEG-AVP0458. If this occurs, the rate of infusion should be decreased or the infusion terminated completely in accordance with the following guidelines:

	Action ¹			
	Decrease rate of	Stop		
Clinical Manifestation	¹²⁴ I-PEG-AVP0458 Infusion by 50%	¹²⁴ I-PEG-AVP0458		
		Infusion ²		
↓ Systolic BP of 25-50 mmHg	X			
↓ Systolic BP of >50 mmHg		X		
Bronchospasm		X		
Severe shortness of breath		X		
Rigors	X			
Chills	X			

- 1 = Investigator discretion is necessary for a decision to reduce the rate or stop ¹²⁴I-PEG-AVP0458 infusion.
- 2 = The infusion may be re-initiated within 1 hour at the discretion of the Investigator. Should the clinical situation require that therapy be stopped again, the ¹²⁴I-PEG-AVP0458 infusion will not be restarted and the patient will be removed from study.

Management of Toxicities 5.9.3

Precautions for anaphylaxis must be available. Equipment for assisted ventilation and an established free flowing line must be available at the time of each infusion.

A life-threatening anaphylactic response of a sensitized human may appear within minutes after administration of a specific antigen and is manifested by respiratory distress often followed by vascular collapse or by shock without antecedent respiratory difficulty. Cutaneous manifestations are exemplified by pruritus and urticaria with or without angioedema and may be characteristic for systemic anaphylactic reactions. Gastrointestinal manifestations may include nausea, vomiting, crampy abdominal pain, and diarrhoea.

Diagnosis of anaphylaxis or choice of treatment and drug dosing is in the responsibility and at the discretion of the individual Investigator.

Appropriate supportive therapeutic interventions may be initiated at any time. Treatment with IV corticosteroids, antihistamines, pethidine, paracetamol, or adrenaline should be considered in the event of an allergic reaction or hypersensitivity. Refer to Appendix 2 for definition of allergic reaction or hypersensitivity according to CTCAE v4.0.

These events will be recorded in the patient's medical history and eCRF.

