5.13 Patient Evaluability

All patients who receive the infusion of ¹²⁴I-PEG-AVP0458 diabody will be evaluable for safety. Every effort will be made to obtain complete information on all AEs, with particular emphasis on serious AEs, infusional toxicities, and hypersensitivity reactions. Patients will be evaluable for biodistribution and pharmacokinetics assessment if they complete all study procedures up to Visit 4 (Day 6 or 7

visit). Patients will be evaluable for immunogenicity of PEG-AVP0458 if they have completed the Day 28 (±2 days) visit procedures.

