8.3 Populations

There will be two populations for consideration.

8.3.1 **Safety Analysis Population**

The safety analysis population includes all patients who were administered study drug and have at least one safety assessment after their infusion.

Evaluable Analysis Population

The evaluable analysis population includes patients who were administered study drug and completed the 4 weeks of scheduled assessments after receiving the infusion.

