Radioactive content in the peripheral blood will be measured by gamma well scintillation counting. Results will be expressed as % injected dose per litre (%ID/L) and µg/mL. PK parameter estimates will also be applied to this data and will be analysed by the Ludwig Institute of Cancer Research. The results will be described in the final study report. Descriptive statistical analysis of data will be performed.

Human Anti-Diabody Antibody (HADA) levels will be measured in serum by ELISA to monitor the immunogenicity associated with the diabody. HADA levels (titres) will be summarised descriptively and listed at each scheduled assessment. The HADA levels will also be graphed over time for each patient, and for each cohort. This analysis will determine whether increased levels of HADA (titres) are potentially associated with adverse events.

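### Sections 5.13 and 8.3.2 contradict each other on who is evaluable, so missing only Day 21 or Day 28 can exclude a patient whose PET data are complete

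*Protocol*

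**What the plan says.** Protocol Section 8.3 opens with "There will be two populations for consideration". One is the safety population. The other, in 8.3.2, is the only set available for anything else: "The evaluable analysis population includes patients who were administered study drug and completed the 4 weeks of scheduled assessments after receiving the infusion". It makes no distinction by endpoint.

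Section 5.13 (Patient Evaluability) sets the rules by endpoint. For PET and PK: "Patients will be evaluable for biodistribution and pharmacokinetics assessment if they complete all study procedures up to Visit 4". For HADA: "Patients will be evaluable for immunogenicity of PEG-AVP0458 if they have completed the Day 28 (±2 days) visit procedures".

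Three other places bear on the point:

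- Section 5.9.2, second footnote to the table: if an infusion has been stopped, restarted and has to be stopped again, the "infusion will not be restarted and the patient will be removed from study".
- Section 5.15: a patient who does not complete the visits over the 4 weeks, for reasons unrelated to study drug, may be replaced.
- Section 8.5, under Secondary Efficacy Assessments, on HADA: "This analysis will determine whether increased levels of HADA (titres) are potentially associated with adverse events". No analysis population is named there, or for the PET and PK analyses.

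**The concern.** The protocol fixes evaluability twice, with different answers. This is not a detail left to a statistical analysis plan: such a plan could follow 5.13 or 8.3.2, but not both.

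The choice matters because the dose groups are tiny. Groups 1 and 2 have 3 patients each, and Section 3.1 bases the dose for the last 6 patients on imaging and pharmacokinetic data. All PET scanning is finished by Visit 4. A set that depends on attendance at Day 21 and Day 28 can therefore remove a patient for a reason that has no bearing on the biodistribution data.

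There is a narrower issue for HADA. Both rules require late attendance. If removal under 5.9.2 ends the visits, a patient whose infusion was stopped twice fails both rules, and the reason for failing is the adverse event itself. The analysis is meant to look for a link between HADA and adverse events, so such a patient should not be lost to it.

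**Working it through.** **Inputs.** The Schedule of Events and Sections 5.2 to 5.8 give the samples and scans. Section 3.1 gives the group sizes (3, 3 and 6), and Section 3.2 gives the total of 12 to 18. No rate of missed visits is stated.

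**The plan's own figure.** Minimum 3 + 3 + 6 = 12. Maximum, with both escalation groups expanded, 6 + 6 + 6 = 18. Both agree with Section 3.2, and this point does not change them.

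**Scheduled data per patient.** Day 0 has 5 PK samples (before infusion, at completion, and 1, 2 and 4 hours later). Visits 1 to 4 add one each.

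| Measurement | Total scheduled | Done by Visit 4 | If only Day 21 or only Day 28 is missed |
|---|---|---|---|
| PET | 5 | 5 | 5 of 5 |
| Gamma counting | 5 + 4 + 1 = 10 | 9 | 10 of 10 |
| ELISA PK | 5 + 4 + 3 = 12 | 9 | 11 of 12 |
| HADA | 5 | 2 | 4 of 5 |

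If the missed visit is Day 14 instead, gamma counting falls to 9 of 10 and PET is still 5 of 5.

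**The two rules applied to the same patient.**

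| Patient | Biodistribution and PK, 5.13 | Immunogenicity, 5.13 | 8.3.2 |
|---|---|---|---|
| Misses only Day 21 | Evaluable | Evaluable | Not evaluable |
| Misses only Day 28 | Evaluable | Not evaluable | Not evaluable |

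The rules disagree for both patients on biodistribution and PK. For the first they also disagree on immunogenicity.

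**Size.** One exclusion from a group of 3 is 1/3 = 33%. For a probability, assume that each of Visits 5, 6 and 7 is missed independently with probability q. The chance that a patient who met the Visit 4 rule fails 8.3.2 is 1 − (1 − q)³. The chance that a group of 3 such patients loses at least one is 1 − (1 − q)⁹.

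| q (assumed) | Patient excluded | At least one of 3 excluded |
|---|---|---|
| 2% | 1 − 0.98³ = 5.9% | 1 − 0.98⁹ = 16.6% |
| 5% | 1 − 0.95³ = 14.3% | 1 − 0.95⁹ = 37.0% |
| 10% | 1 − 0.90³ = 27.1% | 1 − 0.90⁹ = 61.3% |

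**HADA after removal.** A patient removed on Day 0 has a pre-infusion HADA sample (Section 5.2). Section 5.9.2 does not say whether later visits or blood samples take place. If they do not, the patient fails the Day 28 rule in 5.13 and the 4-week rule in 8.3.2. Adopting 5.13 unchanged would therefore not bring the patient back.

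**The case against.** The strongest reply is that nothing in Section 8.5 says the evaluable population will be used for PET, PK or HADA. PK concentrations and HADA titres are graphed for each patient, HADA is listed at every scheduled assessment, and Section 5.10 has the Trial Management Committee work from the data available. All analyses are descriptive, so no test depends on the set, and 5.15 lets unrelated non-completers be replaced. Much of this stands: loss of data is an inference from 8.3.2, not an instruction. But a completer set that is the only non-safety population has little other evident use. Replacement under 5.15 is permitted, not required, and does not cover non-completion related to the drug.

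It is also fair to say that PK is not wholly complete at Visit 4. Gamma counting runs to Day 14 and ELISA to Day 28. Complete is exact for PET, and for gamma counting only if Day 14 was attended.

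On HADA, a reader might infer that patients with infusion reactions in general are filtered out and that the HADA results are therefore biased. The documents do not support that. Only a second stop leads to removal; patients whose rate was reduced, or whose infusion was stopped once and then completed, stay in if they attend. Section 5.9.2 does not say that visits end. A Day 0 reaction also precedes any antibody that the infusion could induce, so the relevant sample is the pre-infusion one. Requiring Day 28 before calling a patient HADA-negative is defensible, since Section 3.1 looks for delayed immunogenic reactions over 30 days. What remains is that a completer rule would leave that pre-infusion sample out of the HADA and adverse event analysis.

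A reader might also set the safety population ("The safety analysis population includes all patients who were administered study drug and have at least one safety assessment after their infusion") against 5.13, which counts everyone infused. The practical difference is close to nil, because vital signs are scheduled at completion of infusion and at 1, 2 and 4 hours afterwards.

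**Conclusion.** The contradiction between 5.13 and 8.3.2 is established from the text. On the natural reading of 8.3.2, a patient who misses only Day 21 or only Day 28 is excluded despite full PET and gamma-counting data and 11 of 12 ELISA samples, which is a third of a 3-patient dose group. The 17% to 61% chance that a group is affected rests on an assumed 2% to 10% miss rate per late visit and on independence between visits; the protocol gives no rate.

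The HADA point is narrower. It concerns only patients removed after a second infusion stop, arises under 5.13 as well as 8.3.2, and depends on whether removal ends assessments, which is unstated. No size can be given for any effect on the HADA results. The matter should be corrected, but it does not threaten the planned number of patients or the primary safety evaluation, since 5.13 and 5.14 keep all infused patients in the latter.

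**What to change.** 1. Replace the single evaluable population in 8.3.2 with endpoint-specific sets that agree with 5.13. For biodistribution and PK, include infused patients with the scans and samples through Visit 4, and use every later sample that exists. For the immunogenicity summary, use one rule, worded identically in both sections.
2. For the analysis relating HADA to adverse events, include all infused patients with any available HADA result, not only those who attend Day 28. A set requiring a post-infusion sample would not be enough, because it could still lose a patient removed on Day 0.
3. Reconcile 5.9.2 with 5.13 and 5.14 by stating whether the scheduled assessments and HADA samples continue after removal following a second stop.
4. In 8.5, name the set used for each secondary analysis.

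The cost is wording. The samples are already scheduled and the number of patients is unchanged. The downside is that some patients will contribute incomplete ELISA or HADA profiles, so each table and graph should show the number with data at each time point.

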8.4 Interim Data Analysis

A Trial Management Committee will be responsible for decisions regarding dose escalation and dose selection. See Section 5.10 on Criteria for Dose Escalation and Dose Selection.

An interim analysis will be performed after the last patient has been enrolled in the second cohort (10mg/m²). Safety and dosimetry data obtained from dose groups 1 and 2 will be analysed and provided to the Trial Management Committee, who will assess which of the two doses, 1 or 10mg/m², will be administered to the last 6 patients (dose group 3) in the study.

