	• Expected survival > 3 months			
	• 18 years or older			

Main Exclusion Criteria	 Undergoing treatment (chemotherapy, immunotherapy or radiation) within 4 weeks of entering this study or planned to receive treatment 		
	within 4 weeks of entering this study of planned to receive treatment within 4 weeks after receiving the study drug		
	Disease-specific criteria		
Study Analyses	Interim analysis after evaluation of the last patient in the second dose		
	level ends		
	Final analysis: at the end of the study		
Study Duration	12 -18 months		
Anticipated Study Start Date	Q1 2012		
Anticipated Enrolment	Q1 2013		
Completion			
Anticipated Study Completion	Q1 2013		

Figure 1. PROTOCOL SCHEMA

- If no patients entered in the 1st dose group experience a dose-limiting toxicity (DLT) (as defined in Section 3.1), then the next dose group may commence 30 days after the last patient on the previous dose group has received the ¹²⁴I-PEG-AVP0458 infusion.
- If any one patient in either cohort of 3 patients experiences a DLT, then 3 additional patients will be entered in that dose group.
- If additional patients are treated in the first dose group, all patients entered must have been observed for 30 days before a new patient may receive an infusion in the second dose group.
- In the event 2 or more patients experience DLT at the first dose level, an additional 3 patients will be entered at a 0.5mg/m² dose level
- Interim analysis will evaluate safety and imaging data available after the dose escalation part of the study and will determine which of the two doses be administered to the last 6 patients in the study. The dose selected will be based on imaging characteristics and pharmacokinetic data of ¹²⁴I-PEG-AVP0458 at each dose level.

TABLE OF CONTENTS

S1	TUDY	PERSONNEL	2
Pı	rotoco	ol Synopsis	6
T/	ABLE (OF CONTENTS	8
A	BBRE\	VIATIONS	12
		ULE OF EVENTS	
1		CKGROUND AND RATIONALE	
	1.1	Ovarian Cancer	
	1.2	Prostate Cancer	
	1.3	AVP0458	
	1.3.1		
	1.	.3.1.1 Expression of TAG-72 in prostate cancer	
	1.	.3.1.2 Expression of TAG-72 in ovarian cancer	18
	1.	.3.1.3 Clinical evaluation of anti-TAG-72 antibodies	18
	1.3.2	2 Antibody based cancer therapy and radioimmunodetection	18
	1.3.3	Recombinant Diabodies	19
	1.3.4	4 AVP0458 Drug Description	19
	1.3.5	Biodistribution of ¹²⁴ I-PEG-AVP0458 in LS174T Xenograft Model	20
	1.4	Rationale for the Study	20
2	STU	JDY OBJECTIVES	20
	2.1	Primary Objective	20
	2.2	Secondary Objectives	20
3	STU	JDY DESIGN	21
	3.1	Summary of Design	21

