As this is a first in-human study, a single subject will receive the first dose of ¹²⁴I-PEG-AVP0458. Further dose administration will be sequential within each cohort to mitigate risks of anaphylactic or any other acute unexpected reactions. Administration of doses within a cohort will be staggered by 24 hours, i.e. there will be a period of 24 hours between the first, second and subsequent subjects in a cohort to observe and interpret reactions and adverse events. This time frame is sufficient to exclude any possible acute allergic or anaphylactic reactions to PEG-AVP0458.

After completion of accrual into the first cohort (1 mg/m 2 dose), the Trial Management Committee will review the safety data from these participants before a decision is made to escalate the dose to 10 mg/m 2 .

If no patients entered in the 1^{st} dose group experience a dose-limiting toxicity (DLT), and the Trial Management Committee agree, then the 2^{nd} dose group may commence on the higher dose of 10 mg/m^2 30 days after the last patient on the first dose group has received the 124 I-PEG-AVP0458 infusion. If any one patient in either cohort of 3 patients experiences a DLT, then 3 additional patients will be entered in that dose group. If additional patients are treated in the 1^{st} dose group, all patients entered must have been observed for 30 days before a new patient may receive an infusion in the 2^{nd} dose group. If greater than or equal to two DLTs are observed at a dose, then the MTD is considered to have been exceeded.

If at most, one DLT is observed, the next 3 patients are assigned to the next highest dose. If two or more DLTs are observed, then the MTD is considered to have been exceeded.

A DLT is defined as any of the following events occurring within 30 days of study drug administration:

- Any Grade 2 or greater allergic reaction.
- Any Grade 3 toxicity. Exceptions are: fever; asymptomatic hyperglycemia; hypophosphatemia; nausea, vomiting, or diarrhoea despite the use of optimal supportive medical therapy; leukopenia or thrombocytopenia that revert to baseline within three weeks of occurrence; lymphopenia without other dose-limiting events (eg opportunistic infection).
- Any Grade 4 toxicity.

The 30 days will allow identification and mitigation of the risks of any delayed immunogenic reaction before progressing to a subsequent cohort.

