In the event 2 or more patients experience DLT at the first dose level, an additional 3 patients will be entered at a 0.5mg/m² dose level.

After the last evaluation of the last patient enrolled in the second dose group (10 mg/m²), an interim analysis of the safety and dosimetry data will be undertaken. This analysis will be considered by the Trial Management Committee to ascertain which of the two doses, 1 or 10 mg/m², produces the better safety profile and dosimetry results for PEG-AVP0458. The dose selected will be based on imaging characteristics and pharmacokinetic data of ¹²⁴I-PEG-AVP0458 at each dose level. This chosen dose will be used to infuse the last 6 patients in the second part of the clinical study. This last group will enrol 3 patients with prostate cancer and 3 with ovarian cancer and will continue to evaluate safety as the primary endpoint.

Because of the low PEG-AVP0458 doses tested in this study, the fact that only two dose levels are being evaluated, and the past clinical experience with the intact parent antibody (CC49), this study is not expected to identify a maximum tolerated dose. It should be noted that the tracer dose of ¹²⁴I-labelled to PEG-AVP0458 has not been reported to be associated with adverse events in prior clinical trials of ¹²⁴I-labelled compounds.

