5.10 Criteria for Dose Escalation and Dose Selection

The Trial Management Committee is responsible for decisions regarding dose escalation (moving dose group 1 to group 2) and dose selection (moving from group 2 to 3), based on safety and dosimetry data.

For dose escalation, the decision is based on safety. If no patients in dose group 1 experience a DLT, then dose group 2 may commence 30 days after the last patient on the dose group 1 has received the PEG-AVP0458 infusion.

If any one patient in either cohort of 3 patients experiences a DLT, then 3 additional patients will be entered in that dose group. If additional patients are treated in the dose group 1, all patients entered must have been observed for 30 days before a new patient may receive an infusion in dose group 2. If greater than or equal to two DLTs are observed at a dose, then the MTD is considered to have been exceeded. If at most, one DLT is observed, the next 3 patients are assigned to the next highest dose. If two or more DLTs are observed, then the MTD is considered to have been exceeded.

In the event 2 or more patients experience DLT at the first dose level, an additional 3 patients will be entered at a 0.5mg/m² dose level

The Trial Management Committee will evaluate safety and dosimetry data available after the dose escalation part of the study (Interim Analysis) and determine the dose to be administered to the last 6 patients in the study.

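### Section 8.4 allows the dose-selection interim once the last dose group 2 patient is enrolled, about four weeks before the trigger in 3.1 and the synopsis, and the sections do not agree on whether PK is part of the data

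*Protocol*

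**What the plan says.** The protocol places the interim that picks the group 3 dose at two different times.

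- Section 8.4: "An interim analysis will be performed after the last patient has been enrolled in the second cohort" (the 10 mg/m² cohort).
- Section 3.1: "After the last evaluation of the last patient enrolled in the second dose group".
- Synopsis, Study Analyses: "Interim analysis after evaluation of the last patient in the second dose" level ends.

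The schema and 5.10 name no visit. Both refer to data available once the escalation part is over; the schema reads "Interim analysis will evaluate safety and imaging data available after the dose escalation part of the study".

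The data on which the choice rests also vary. Section 8.4 states: "Safety and dosimetry data obtained from dose groups 1 and 2 will be analysed and provided to the Trial Management Committee". Section 5.10 likewise names safety and dosimetry. Section 3.1 first describes an interim on safety and dosimetry, then two sentences later says: "The dose selected will be based on imaging characteristics and pharmacokinetic data". The schema has the same pattern, with safety and imaging for the interim and then imaging and PK for the selection.

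The DLT window is 30 days: "A DLT is defined as any of the following events occurring within 30 days of study drug administration". The last scheduled visit is Day 28 (±2), in 5.8.

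**The concern.** The interim fixes the dose for 6 of the 12–18 patients in a first-in-human study. Section 8.4 is where an analyst would look for the rule, and its trigger can be met before the last group 2 patient has any post-infusion data. The protocol ties enrolment to assignment to treatment (7.2.1) or to receipt of study drug (6.1), and on either meaning that patient has no follow-up at the trigger.

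The trigger is also hard to apply. One DLT among the first three patients adds three more to the group, and a DLT can arise up to 30 days after dosing. At enrolment of the third patient it is therefore not yet known whether that patient is the last in group 2, or whether two or more DLTs will put 10 mg/m² above the maximum tolerated dose.

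If PK is a selection criterion in one place and absent from the committee's package in another, the basis of the choice is not fixed in advance.

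**Working it through.** **Passages side by side**

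| Place | Earliest time of interim | Data named |
|---|---|---|
| 8.4 | Last group 2 patient enrolled | Safety, dosimetry |
| 3.1 | Last evaluation of last group 2 patient | Safety, dosimetry; then imaging, PK |
| Synopsis, Study Analyses | End of evaluation of last group 2 patient | None named |
| Schema | After the escalation part | Safety, imaging; then imaging, PK |
| 5.10 | After the escalation part | Safety, dosimetry |

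The last evaluation falls on Day 26 to Day 30, so the triggers in 8.4 and 3.1 differ by about four weeks.

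**What exists at the 8.4 trigger**

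Inputs from the protocol:
- Group 2 has 3 patients, with doses at least 24 hours apart (3.1).
- The DLT window is 30 days (3.1, 6.1).
- Each patient has 5 PET scans: Days 0, 1, 2 or 3, 4 or 5, and 6 or 7.
- Each patient has 12 ELISA PK samples: 5 on Day 0, then Days 1, 2 or 3, 4 or 5, 6 or 7, 14, 21 and 28.
- Evaluability for biodistribution and PK requires all procedures through Visit 4, Day 6 or 7 (5.13).

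Assumption: the gap *g* between patients. Only the 1-day minimum is stated; 7, 24 and 30 days are assumed. The 24-day value comes from the 9-month accrual in 3.3: 9 × 30.44 = 274 days. Taking off 60 days for two changes of dose group leaves 214 days over 2 + 2 + 5 = 9 within-group gaps for 12 patients, or about 24 days each.

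At enrolment of the third patient the elapsed times are 2*g*, *g* and 0 days. DLT patient-days observed = min(2*g*, 30) + min(*g*, 30) + 0, out of 3 × 30 = 90. Assessments due on the day count as done, and the last patient counts as contributing none.

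| Gap (days) | DLT patient-days of 90 | PET of 15 | ELISA PK of 36 | Full PET series | Past 30 days |
|---|---|---|---|---|---|
| 1 | 2 + 1 + 0 = 3 (3%) | 4–5 | 12–13 | 0 of 3 | 0 of 3 |
| 7 | 14 + 7 + 0 = 21 (23%) | 10 | 19 | 2 of 3 | 0 of 3 |
| 24 | 30 + 24 + 0 = 54 (60%) | 10 | 23 | 2 of 3 | 1 of 3 |
| 30 | 30 + 30 + 0 = 60 (67%) | 10 | 24 | 2 of 3 | 2 of 3 |

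At the 1-day gap no patient has reached Visit 4, so none is evaluable under 5.13. However wide the gap, the last patient's third of the data is missing. If group 2 is expanded to 6, PET stands at 14–16 of 30 at 1-day gaps and 25 of 30 at gaps of 7 days or more.

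**What exists at the 3.1 trigger**

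If every patient completes, all 15 of 15 scans and 36 of 36 ELISA samples exist. The last patient's DLT window can still be open by 30 − 30 = 0 to 30 − 26 = 4 days.

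**The case against.** A reader might infer from 8.4 that the dose would be chosen with no group 2 safety, PET or PK data at all. The documents do not support that. The next sentence of 8.4 calls for group 2 data to be analysed. Dosing is staggered, so earlier group 2 patients already have some data. And a rule that begins with the word after sets only an earliest time: an interim held after the last evaluation satisfies 8.4 too. Section 8.4 also refers to 5.10, which speaks of data available after escalation. With 3.1, the synopsis and the schema, four other places give a coherent later reading.

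Two further inferences would go too far. This interim is not the trial's only data-driven decision, because escalation from group 1 to group 2 also rests on observed safety. Nor is it settled that no 30-day wait applies between groups 2 and 3. The explicit waiting rules cover only group 1 to group 2, but 3.1 gives the purpose of the 30 days as catching delayed immune reactions before moving to a later cohort, without limiting this to group 1. AEs are in any case recorded to 30 days (6.1).

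The data-package mismatch is not simply 3.1 against 8.4, since it also lies within 3.1 and within the schema, and 8.4 does not expressly exclude PK. The analyses are descriptive, so no error rate or power is at stake.

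These arguments limit the severity. They do not remove the contradiction: 8.4 permits an interim that 3.1 and the synopsis do not.

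**Conclusion.** The inconsistency is real and of moderate severity. Read literally, 8.4 permits group 3 dose selection on incomplete group 2 data, always without follow-up from the last patient. At the permitted minimum stagger it leaves 3% of DLT patient-days, 4–5 of 15 PET scans and no evaluable patient. At assumed gaps of 7 to 24 days it leaves 23% to 60% of patient-days and two thirds of the scans. These sizes depend on the spacing between patients, for which the protocol states only the minimum, and on the interim being run at the earliest time that 8.4 allows.

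Separately, PK is a stated selection criterion in 3.1 and the schema but is not named in the package described in 8.4 and 5.10. The 30-day DLT window, its stated purpose, the Day 28 (±2) last visit and the between-group waiting rules also do not fit together fully. The residual for the last patient under the 3.1 trigger is 0–4 days.

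**What to change.** 1. Change the 8.4 trigger to match 3.1 and the synopsis: the interim follows the last evaluation of the last dose group 2 patient, including any patient added after a DLT.
2. Name one data package in 8.4, 3.1, 5.10 and the schema, including the PK data that 3.1 makes a selection criterion alongside safety and imaging/dosimetry.
3. Reconcile the 30-day DLT window and its stated purpose with the Day 28 (±2) last visit and with waiting rules that are explicit only for group 1 to group 2. How to resolve this is for the sponsor and the investigators.

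Items 1 and 2 cost an amendment to wording, with ethics committee approval under 11.1. Item 1 adds no time beyond what 3.1 already requires. Any cost of item 3 depends on how it is resolved; under the 3.1 trigger at most 4 days of the last patient's window are open.
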